PROTOCOL FOR PIVOT PILOT STUDY:
PATIENT INFORMATION VIDEOS ON OPERATIONS TRIAL

SUMMARY

Patient education is an important part of preparing patients for surgical procedures. This pilot project aims to determine the use of two educational videos created by specialists for patients due to have either an elective caesarean section or a trans-vaginal tape / trans-obturator tape. This pilot study aims to gather the information required to undertake a larger scale study which will assess whether there is a relationship between preoperative anxiety levels and education on the procedure when the educational video is used as an information giving tool alongside existing resources. A total of 120 patients will be enrolled (60 per group) and randomised to either watch the video or not watch the video. Assessment will be done by means of a questionnaire, and results will be collected over the course of eight months. It is expected that the video may reduce anxiety in preoperative patients and that they may feel better informed about the reason for the operation, the procedure and the post-operative period.

RESEARCH QUESTION

Does the additional use of multimedia provide a more effective means of educating the patient on risks and benefits of a common elective surgical procedure as well as reduce overall pre-operative anxiety?

RATIONALE & BACKGROUND INCLUDING LITERATURE REVIEW

While patients are always explained the key risks and complications of any elective surgical intervention, they often feel unprepared for both the hospital stay and the postoperative period.^{1,2} Multimedia has already been used in randomised trials as a means of delivering information to patients preoperatively to reduce overall anxiety regarding the procedure.^{2,3,4}

Currently in the NHS patient information regarding surgical procedures is delivered through tools such as leaflets in combination with consultations where the patient is able to ask questions. A video is a concise learning tool which the patient would be able to access 24/7 and also show their relatives. This would not only allow them enough time to think through the possible complications but also to inform them of accurate and up to date information which is included in the consent forms they are presented pre-operatively.

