A learning needs assessment where patients were approached post-operatively in Royal Devon and Exeter Trust, Wonford Hospital and asked to complete a questionnaire regarding pre-operative knowledge and anxiety highlighted certain points which patients felt they would have liked to have been informed of sooner. For example patients who had undergone a C-section commented that side effects of the anaesthetic were not fully explained and therefore not expected, and this was subsequently included in the video for this patient group. Other comments from the TVT/TOT post-operative patients involved a request for a detailed explanation of urinary incontinence and treatment options, including recovery time. Every effort was made to include the feedback from patients as points to cover in the educational videos created.

This study aims to highlight the benefit of provision of a cheap and accurate information tool in the form of a video designed to complement existing methods of preparing patients for elective surgical admissions. The ultimate goal is to prepare a database of a selection of videos accessible to patients in their own home at any time. The videos will be

monitored and updated, and any videos submitted to the website will be assessed by two specialist consultants for accuracy prior to being added to the database.

AIMS AND OBJECTIVES

Aim: Determine whether educational videos are of use as an additional learning resource for pre-operative patients.

Objectives:

- 1- Quantify the change between baseline patient anxiety and operative knowledge at preoperative assessment, compared to immediately pre-operatively in intervention and control group.
- 2- Record the relative change in anxiety level of pre-operative consented patients who have seen the video to those who have not using a ten point visual analogue scale and the State Trait Anxiety Inventory.
- 3- Record the relative change in knowledge base of pre-operative consented patients who have seen the video to those who have not. Specifically these headings will be assessed:
 - The condition
 - The operation
 - The risks and complications
 - The post-operative period

Secondary Objectives:

- 1- Receive verbal and written feedback on the videos in order to improve them
- 2- Test data collection methods, especially questionnaires.
- 3- Assess recruitment rate
- 4- Test the delivery of the video
- 5- Get an estimate of standard deviation of the outcome measures.

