Data management and statistical analysis

Patient consent forms and questionnaires will be filed securely in a padlock protected

locker at the Research and Development Building, Wonford.

No patient identifiers will be recorded on home laptops or home computers.

The data will be assimilated in an Excel Sheet and stored on a password protected computer/laptop.

Consent forms will be held for 3-6 months and then destroyed.

Additional data will be held for 5 years.

All Data Protection guidelines and the Data Protection act will be adhered to for confidentiality purposes.

The trust statistician will be approached for advice on randomisation of the opaque envelopes.

The person who undertakes the role of randomisation will be recorded in the research study log.

Descriptive statistics of baseline characteristics will be compared between study groups to demonstrate the effectiveness of randomisation. Categorical data will be summarised as proportions and percentages as appropriate with associated confidence intervals. No attempt will be made at this stage to make formal comparisons of outcome measures – this will be done in the eventual definitive study. Summaries of secondary outcome measures will also be produced in a similar manner to the above.

PROJECT MANAGEMENT

Personnel

Producing the video:

Animator: Consultant Anaesthetist

Producer and Voiceover: Consultant Obstetrician & Gynaecologist

Camerawoman and Editor: Communications and Corporate Affairs Officer

Writer, Director and Researcher, Creation of Storyboards: Year 5 Intercalating Medical Student (2011/12)

Quality Control: Trust Communications Manager

The Study

There will be four delegates:

Chief Investigator: Consultant Obstetrician & Gynaecologist.

Co-Investigator: Foundation Year 1 Doctor, RD&E (2013-14)

2x Sub-Investigators: Until December 2012: Clinical Medical Student and Foundation doctor

From July 2013: Research nurse and research midwife

Statistician: Hospital Trust Statistician

Project Responsibilities:

Data storage/monitoring: Sub-Investigators

Consenting: Sub-Investigators

Recruitment: Sub-Investigators

Statistical advice: Hospital Trust Statistician

Data analysis: Co-investigator

Write-up: Co-investigator and Chief Investigator

Additional Training Required: For the Sub-Investigators, if not already obtained, GCP Training will be required.

*First Main Contact for the Study: [name], Foundation Year 1 Doctor, RD&E.
[contact], [name]*

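### Does the absence of a named summary for the numeric outcome scores leave the pilot's standard deviation undefined?

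*Combined protocol and SAP*

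**What the plan says.** The whole analysis plan is one short paragraph under Data management and statistical analysis. It has four elements:

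- Baseline: "Descriptive statistics of baseline characteristics will be compared between study groups to demonstrate the effectiveness of randomisation".
- Categorical data: "Categorical data will be summarised as proportions and percentages as appropriate with associated confidence intervals".
- Outcome comparisons: "No attempt will be made at this stage to make formal comparisons of outcome measures"; these are left to the definitive study.
- Secondary outcomes: "Summaries of secondary outcome measures will also be produced in a similar manner to the above".

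Under Aims and Objectives, objectives 1 to 3 concern the change in anxiety and knowledge from pre-operative assessment to the day of operation, set against each other in the video and control arms. Knowledge is to be looked at under four topics ("Specifically these headings will be assessed"). Secondary objective 5 is to estimate the SD of the outcomes. The Summary gives the pilot's purpose as to "gather the information required to undertake a larger scale study", and its size as follows: "A total of 120 patients will be enrolled (60 per group) and randomised to either watch the video or not watch the video". The later target list gives 30 per arm within each of the two operations.

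**The concern.** No mean, SD or median is named for any numeric outcome, and the instruction to treat secondary outcomes like what precedes them points back to a rule for categorical data. Secondary objective 5 therefore leaves two things unstated:

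- **Which SD.** It could be that of the follow-up score, of the change, or of the residual after baseline adjustment.
- **Which patients.** It could be calculated within each operation or over both. The word group serves for arm in some places and operation in others, and 60 per group in the Summary fits either reading.

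The SD is meant to feed the larger study. If one unlabelled value were reported, a planner could mistake one variance for another and mis-size that trial. Scoring raises a related doubt. No text assigns items to the four knowledge topics, the readiness item has no obvious home, and the item on unanswered questions runs in the opposite direction to the others.

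**Working it through.** **1. The plan's own figure.** 2 operations × 2 arms × 30 = 120, which matches the stated enrolment. The protocol gives no SD, effect size, significance level or power, so there is no other calculation to reproduce.

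**2. Which SD do the objectives imply?** All three main objectives are framed as change, compared by arm. The natural outcome measure is the change score, and its SD is the first candidate. Residual SD appears nowhere in the protocol.

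**3. What does group mean in the analysis paragraph?** The comparison is there to show that randomisation worked. Operation is not randomised, so these groups can only be arms. The other use, in the filing instructions of Stage 2, is a label for wallets.

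**4. By operation or pooled?** Targets, videos, questionnaires and number ranges (001–060 for tape procedures, 061–120 for caesarean) are separate. The caesarean form has items of its own, such as breastfeeding. Nothing proposes pooling.

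**5. Is anything lost?** Numbers are matched across the consent form and both questionnaires, the number itself identifies the operation, and allocation is added before the data reach the statistician (Stage 3). As to retention, "Additional data will be held for 5 years". With s0 and s1 the SDs at the two stages and sd the SD of change:

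- correlation r = (s0² + s1² − sd²) / (2·s0·s1)
- residual variance = s1²(1 − r²)

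For example, s0 = s1 = 1 and sd² = 1.40 give r = (2 − 1.40)/2 = 0.30 and residual variance 1 − 0.09 = 0.91. Ordinary SDs at each stage and of the change therefore yield the planning quantity as well.

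**6. What would confusing them cost a later trial?** This is an illustration on assumptions that are not in the protocol: equal variance of 1 at both stages, a target difference of 0.5 follow-up SD, two-sided 5% and 80% power. Then n per arm = 2(1.960 + 0.842)²·variance/0.5² ≈ 62.8 × variance, rounded up. Change variance is 2(1 − r).

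| r | Follow-up variance (n) | Change variance (n) | Residual variance (n) |
|---|---|---|---|
| 0.3 | 1.00 (63) | 1.40 (88) | 0.91 (58) |
| 0.5 | 1.00 (63) | 1.00 (63) | 0.75 (48) |
| 0.7 | 1.00 (63) | 0.60 (38) | 0.51 (33) |

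Pooling operations whose means differ by d within-operation SDs (equal numbers and SDs assumed) multiplies the variance by 1 + d²/4: 1.02, 1.06 and 1.25 for d = 0.25, 0.5 and 1.0.

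**7. Sampling error, for scale.** With all 60 per operation complete and two arm means removed (58 df), the 95% limits for an SD are √(58/χ²), or 0.85 to 1.22 times the estimate. In sample-size terms (squared) that is 0.72 to 1.49. This uncertainty comes from the pilot's size and is the same whichever SD is named. The protocol's 3/10 for refusal or loss is applied to the eligible pool: 120 × 0.7 = 84 and 150 × 0.7 = 105, both above 60. It mixes refusal with drop-out, so the number completing both stages is not known.

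**The case for a change.** The best case for a change is that, with formal comparisons deferred, descriptive estimates are the pilot's main statistical output, so the one paragraph on analysis should name them. Nor is it certain that a statistician will settle the matter. Stage 3 sends the data to the statistician for analysis, but the list of project responsibilities gives data analysis to the co-investigator and only advice to the statistician. A written line would cost little.

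Part of this stands. The omission is real, and a report that labels each SD and gives it by arm within operation will be more useful than one that does not. However, that is ordinary reporting practice. The remaining harm needs a report with a single unlabelled or pooled SD, which no text proposes.

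The scoring doubts carry less weight. A point-scoring system is planned, the protocol calls the questionnaires drafts, and testing them is secondary objective 2. The forms are also incomplete in the text available here, so the absence of an item map cannot be asserted. Readiness could reasonably sit under the operation, and the reversed item is plain from its own end labels.

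**Conclusion.** No change to the plan follows. The analysis paragraph leaves out a detail that an analyst would supply from the objectives and the design: means and SDs at each stage and of the change, by arm within operation. No stated rule gives a wrong answer if followed. No pilot result or conclusion depends on the choice, and any of the SDs can be produced later from the retained data.

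The differences shown (63 per arm against 88 to 38 for a change SD, or 58 to 33 for a residual SD) rest on assumed correlations, equal variances and an assumed target difference. They measure the cost of misreading a label in a later trial, not an error in this one. The conclusion assumes that both questionnaires are scored on common items within each operation, which the incomplete forms do not allow to be confirmed.

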Moderately ready

Extremely ready

Do you feel you know what to expect in the operating theatre?

1	2	3	4	5	6	7	8	9	10

Not at all

Moderate

Extremely Well

Do you feel you understand what the surgeon will do in the operation?

1	2	3	4	5	6	7	8	9	10

Not at all

Moderately informed

Extremely Well Informed

Do you know how your anaesthetic will be given to you?

1	2	3	4	5	6	7	8	9	10

Not at all informed

Moderately informed

Extremely Well Informed

How well do you think you have been informed of the side effects of the anaesthetic?

1	2	3	4	5	6	7	8	9	10

Not at all informed

Moderately informed

Extremely Well Informed

Are you aware of the possible complications and risks involved in your operation?

1	2	3	4	5	6	7	8	9	10

Not at all informed

Moderately informed

Extremely Well Informed

Do you know how long you are likely to stay in hospital?

1	2	3	4	5	6	7	8	9	10

Not at all

Moderately aware

Extremely aware

How well do you feel you have been explained the benefit and success rate of the operation?

1	2	3	4	5	6	7	8	9	10

Not at all

Moderately

Extremely well

How well informed do you feel about your recovery period after the operation?

1	2	3	4	5	6	7	8	9	10

Not at all informed

Moderately informed

Extremely Well Informed

Do you feel you have questions you would have liked to have asked that have not been answered?

1	2	3	4	5	6	7	8	9	10

Not at all

Some questions

A lot of questions

Many thanks for your time and honesty. This completes the questionnaire, and we look forward to seeing you again soon, to complete the second stage of the project.

Best wishes,

[name]
Co-Investigator for PIVOT Study

PIVOT: Patient Information Videos on Operations Trial

Patient Education on Common Surgical Procedures: Using Rapid Sequence Animation Videos

QUESTIONNAIRE 1 : to be completed by the patient after verbal consent gained by research midwife, approximately three weeks before the operation (stage 1)

Operation: ELECTIVE CAESAREAN SECTION

Participant Number:	061
---------------------	-----

ABOUT YOU

1- Please select the appropriate box for each category:

Age

<24	25-29	30-39	40-49	>50

Education Level

Secondary school	GCSEs	College / A - levels	Diploma	Undergraduate degree	Postgraduate degree

Employment status (when not on maternity leave)

Unemployed	Employed	Student	Other

Do you work in healthcare?

Yes		No	
-----	--	----	--

Have you had this operation before?

Yes		No	
-----	--	----	--

1	2	3	4	5	6	7	8	9	10

Not at all informed

Moderately informed

Extremely Well Informed

How aware are you of the long term implications of having a c-section?

1	2	3	4	5	6	7	8	9	10

Not at all

Moderately aware

Extremely aware

Do you know how long you are likely to stay in hospital?

1	2	3	4	5	6	7	8	9	10

Not at all

Moderately aware

Extremely aware

How well informed do you feel about your recovery period after the operation?

1	2	3	4	5	6	7	8	9	10

Not at all informed

Moderately informed

Extremely Well Informed

Do you feel you have questions you would have liked to have asked that have not been answered?

1	2	3	4	5	6	7	8	9	10

Not at all

Some questions

A lot of questions

Many thanks for your time and honesty. This completes the questionnaire, and we hope you have a quick recovery from your operation!

Best wishes,

[name]
Co-Investigator for PIVOT Study

PIVOT: Patient Information Videos on Operations Trial

**Patient Education on Common Surgical Procedures:
Using Rapid Sequence Animation Videos**

QUESTIONNAIRE 2 : to be completed on the day of the operation (Stage 2)

Operation: TRANS-VAGINAL / TRANS-OBTURATOR TAPE

Participant Number:	001
---------------------	-----

The questionnaire is three pages long, and should take approximately 15 minutes to complete.

Please turn over to start the questionnaire.

B- PREOPERATIVE KNOWLEDGE**How informed do you feel about your condition?**

1	2	3	4	5	6	7	8	9	10

Not at all informed

Moderately informed

Extremely Well Informed

How informed do you feel about the reasons why this operation has been offered to you?

1	2	3	4	5	6	7	8	9	10

Not at all

Moderately informed

Extremely Well Informed

Do you feel ready for the operation?

1	2	3	4	5	6	7	8	9	10

Not at all ready

Moderately ready

Extremely ready

Do you feel you know what to expect in the operating theatre?

1	2	3	4	5	6	7	8	9	10

Not at all

Moderate

Extremely Well

Do you feel you understand what the surgeon will do in the operation?

1	2	3	4	5	6	7	8	9	10

Not at all

Moderately informed

Extremely Well Informed

Do you know how your anaesthetic will be given to you?

1	2	3	4	5	6	7	8	9	10

Not at all informed

Moderately informed

Extremely Well Informed

How well do you think you have been informed of the side effects of the anaesthetic?

1	2	3	4	5	6	7	8	9	10

Not at all informed

Moderately informed

Extremely Well Informed

Are you aware of the possible complications and risks involved in your operation?

1	2	3	4	5	6	7	8	9	10

Not at all informed

Moderately informed

Extremely Well Informed

PIVOT: Patient Information Videos on Operations Trial

**Patient Education on Common Surgical Procedures:
Using Rapid Sequence Animation Videos**

QUESTIONNAIRE 2 : to be completed on the day of the operation (Stage 2)

Operation: ELECTIVE CAESAREAN SECTION

Participant Number:	061
---------------------	-----

The questionnaire is three pages long, and should take approximately 15 minutes to complete.

Please turn over to start the questionnaire.

Do you know when you can start breastfeeding your baby?

1	2	3	4	5	6	7	8	9	10

Not at all informed

Moderately informed

Extremely Well Informed

How aware are you of the long term implications of having a c-section?

1	2	3	4	5	6	7	8	9	10

Not at all

Moderately aware

Extremely aware

Do you know how long you are likely to stay in hospital?

1	2	3	4	5	6	7	8	9	10

Not at all

Moderately aware

Extremely aware

How well informed do you feel about your recovery period after the operation?

1	2	3	4	5	6	7	8	9	10

Not at all informed

Moderately informed

Extremely Well Informed

Do you feel you have questions you would have liked to have asked that have not been answered?

1	2	3	4	5	6	7	8	9	10

Not at all

Some questions

A lot of questions

Many thanks for your time and honesty. This completes the questionnaire, and we hope you have a quick recovery from your operation!

Best wishes,

[name]
Co-Investigator for PIVOT Study
